5.2 Participant Disposition

To assess the impact of COVID-19, a table based on the ITT (overall and by IMP) for each country (and overall) will indicate the number of participants at each visit performed, number of participants with missed visits, number of participants with telephone calls or video calls performed. Corresponding listing will be created in ES.

A separate table by IMP for the Main and Extension Portion will provide details on subjects discontinued due to AEs. More precisely, the number and percentage of participants who discontinued the study due to AE (AEs leading to discontinuation of only the following type: serious fatal, non-fatal, non-serious fatal) will be presented.

5.3 Primary Endpoint(s) Analysis

- Treatment: Zilucoplan administered by daily subcutaneous (SC) injection (0.3 mg/kg) vs matching placebo
- Target Population: is defined through the inclusion/exclusion criteria at Sections 8.1 and 8.2 of the study protocol reflecting the targeted IMNM population
- Endpoint: percentage change from baseline to Week 8 in CK levels
- Intercurrent event handling: regardless of any treatment discontinuation for any reason; censoring after prohibited medication
- Population level summary: difference in ranks of the percentage change from baseline between treatments followed by the Wilcoxon-Mann-Whitney odds (WMWodds) and Hodges–Lehmann estimator.

The statistical hypothesis being tested at Week 8 is that there is no difference in the percentage change from baseline in CK levels between Zilucoplan and placebo as described at Section 2.1.

5.3.1 Definition of endpoint(s)

The primary endpoint is the percentage change from baseline of CK levels at Week 8, defined as:

$$\%CHG = 100 \times (\text{Value}_{\text{WEEK8}} - \text{Value}_{\text{BSL}}) / \text{Value}_{\text{BSL}}$$

5.3.2 Main analytical approach

The statistical hypothesis is stated at Section 2.1. The analysis will be conducted in the ITT using a 2-sided Van Elteren test (Van Elteren, 1960) which stands for an extension of the Wilcoxon rank sum test for comparing two treatments in a stratified experiment using within-stratum ranks assigning greater weight to rank sums from smaller strata.

The magnitude of association between groups will be expressed as in WMWodds followed by the 95% CI and by the Hodges–Lehmann estimator which quantifies the location shift.

WMWodds will be estimated based on the weighted average WMWodds for the strata. The methodology is described below:

- For each stratum the WMWOdds will be calculated via ROC analysis for the CK levels.
- The derived AUC and SE values will be used for the calculation of the stratified WMWOdds:
 $WMWodds_i = AUC_i / (1 - AUC_i)$, $i = 1, 2$

The WMWodds_i and the Standard Error (SE) will be transformed to the logarithmic scale to ensure positive values of the corresponding 95%CIs:

$$\text{LnWMWodds}_i = \text{Ln}(AUC_i / (1 - AUC_i)), i = 1, 2$$

$$\text{LnSE}_i = \text{SE}_i / (AUC_i * (1 - AUC_i)), i = 1, 2$$

- Inverse variance weights will be assigned at each strata: $W_i = 1 / (\text{LnSE}_i * \text{LnSE}_i)$, $i = 1, 2$:
- The weighted average WMWodds ($\overline{WMWodds}$) and the corresponding 95%CI can be then calculated as shown below:

$$\overline{WMWodds} = \exp \left(\frac{\sum_{i=1}^2 W_i * \text{LnWMWodds}_i}{\sum_{i=1}^2 W_i} \right)$$

$$95\%CI = \exp \left(\left(\frac{\sum_{i=1}^2 W_i * \text{LnWMWodds}_i}{\sum_{i=1}^2 W_i} \right) \pm Z_{0.025} * 1 / \sqrt{\sum_{i=1}^2 W_i} \right)$$

Additionally, for the unweighted WMWodds and Hodges–Lehmann estimator followed by the corresponding 95%CI, will also be calculated.

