12.2.5.1 PRIMARY EFFICACY ANALYSES

The primary efficacy endpoint, percent reduction from baseline in creatine kinase at Week 8, will be compared between the two treatment groups using a 2-sided stratified Wilcoxon rank sum test (Van Elteren test). Magnitude of treatment effect will be shown by the WMWodds and the Hodges-Lehman estimator followed by the corresponding 95% Confidence Intervals (CIs).

Definition of primary estimand:

- Treatment: zilucoplan administered by daily SC injection (0.3 mg/kg) vs matching placebo.
- Target Population: is defined through the inclusion/exclusion criteria at Sections 8.1 and 8.2 of the study protocol reflecting the targeted IMNM population.
- Endpoint: percentage change from Baseline to Week 8 in CK levels while on non-prohibited medication.
- Intercurrent event: regardless of any treatment discontinuation for any reason; censoring after prohibited medication
- Population level summary: difference in ranks of the percentage change from baseline between treatments followed by the WMWodds and Hodges–Lehmann estimator followed by the corresponding 95% CIs.

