2.1 Primary endpoint

The Null Hypothesis for the primary endpoint is that there is no treatment difference in Week 8 between Zilucoplan and placebo treatment conditions in the percentage change from baseline of CK levels.

The Null Hypothesis (H_{01}) asserts that it is equally likely to one treatment group to be less than or greater than the other splitting ties evenly:

Let Y_1 and Y_2 be observations drawn independently from the two IMP (Investigational Medicinal Products) distributions.

Then:

- H_{01} : $\pi = 0.5$ for both strata, where $\pi = \text{Prob}(Y_1 < Y_2) + 1/2 \text{ Prob}(Y_1 = Y_2)$ and
- H_{A1} : $\pi_i \neq 0.5$ for at least one stratum (Alternative Hypothesis)

Converting π to an odds measure: $WMWodds = \pi / (1 - \pi)$ the H_{01} and H_{A1} can be re-written as:

- H_{01} : $WMWodds = 1$
- H_{A1} : $WMWodds \neq 1$

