3 SAMPLE SIZE DETERMINATION

A sample size of 12 study participants per group yields approximately 95% power to detect a difference in the percent reduction from baseline in creatine kinase between the active and placebo groups using a Wilcoxon rank sum test at the two-sided 0.05 type 1 error rate.

The power calculations assume that the percent reduction in creatine kinase in the active dose group is approximately normally distributed with a mean of 80% and a standard deviation of 8%; that 4 of the placebo patients will have a percent reduction similar to the active dose group; and the remaining 8 placebo patients will have a percent reduction that is normally distributed with a mean of 10% and a standard deviation of 8% (Mammen and Timakou 2015).

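### SAP 5.3.2 tells the programmer to compute the primary WMWodds from CK levels, while the hypothesis, endpoint and estimand it quantifies use percent change; the wording needs reconciling

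*SAP*

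**What the plan says.** SAP 5.3.1 fixes the variable: "The primary endpoint is the percentage change from baseline of CK levels at Week 8", followed by the formula for %CHG. SAP 2.1 states the null as no difference between the zilucoplan and placebo "treatment conditions in the percentage change from baseline of CK levels". In the same place it defines WMWodds as π/(1−π) and restates the null as WMWodds = 1. The estimand in SAP 5.3 (and Table 1-1) takes ranks of the percentage change and then the WMWodds and Hodges–Lehmann estimator. Protocol 12.2.5.1 follows its test on percent reduction with this: "Magnitude of treatment effect will be shown by the WMWodds and the Hodges-Lehman estimator".

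SAP 5.3.2 gives the method. The test is set out first: "The analysis will be conducted in the ITT using a 2-sided Van Elteren test". The WMWodds is then built stratum by stratum: "For each stratum the WMWOdds will be calculated via ROC analysis for the CK levels". The AUC and its SE from that step feed the log odds, the inverse-variance weights, the pooled WMWodds and its 95% CI. No other instruction for computing the WMWodds appears in the SAP. SAP 5.3.4 reuses 5.3.2 for the LOCF, per-protocol and no-COVID repeats and for the Week 4 analysis (A). SAP 6.3 declares no change from the protocol-planned analyses.

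**The concern.** The step that produces the number names a different variable from the one the number is meant to describe. CK at Week 8 carries the between-patient spread of baseline CK, which percent change divides out. Entry requires only CK above 1000 U/L at Screening, with no upper limit. Taken literally, the test would concern percent change while its companion effect size and CI concerned CK level. The effect size would on average be pulled toward 1 by baseline spread, and a chance imbalance in baseline CK could shift it in either direction. The sentence also leaves the visit and the direction of the AUC unstated. According to SAP Section 1, a contract research organization does the analysis from the protocol and the SAP, so the calculation step should not need interpretation.

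**Working it through.** **Inputs from the documents.** SAP 3 and protocol 12.3: 12 per arm; percent reduction on active normal, mean 80, SD 8; 4 of 12 placebo patients like active; the other 8 normal, mean 10, SD 8; two-sided 0.05. Protocol 8.1: CK above 1000 U/L at Screening.

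**Assumptions.** Baseline CK log-normal, median 5000 U/L, truncated at >1000 U/L, log-SD 0.3 to 1.3. For the CI only: strata of 6+6 per arm and a nonparametric SE for the AUC. The documents give none of these.

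**1. The plan's own figure.** Simulating 20,000 trials with the exact rank sum test (reject at U ≤ 37, attained level 0.0449) gives 94.8% power, against the stated approximately 95%. The planning model is therefore read correctly, and this figure does not depend on the disputed sentence.

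**2. WMWodds on percent change.** Let π be the chance that an active patient has the lower value.
- Against a placebo responder: 0.5.
- Against a placebo non-responder: Φ((80 − 10)/(8√2)) = Φ(6.19) ≈ 1.
- π = 1/3 × 0.5 + 2/3 × 1 = 0.833, so WMWodds = 0.833/0.167 ≈ 5.0, whatever the baseline CK.

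**3. WMWodds on Week 8 level.** Week 8 CK = baseline × (1 − reduction). Against a responder, π stays at 0.5. Against a non-responder, the log-scale gap is ln(0.90/0.20) = 1.504, now set against baseline spread σ in both patients. A hand approximation at σ = 1.0, ignoring truncation and the SD of 8:
- Φ(1.504/(√2 × 1.0)) = Φ(1.064) = 0.856.
- π = 0.167 + 2/3 × 0.856 = 0.737, so WMWodds ≈ 2.8.

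Truncation at 1000 U/L narrows the spread, and simulation then gives about 3.0.

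**4. The SAP's interval.** In each stratum, LnWMWodds = ln(AUC/(1 − AUC)) and LnSE = SE/(AUC × (1 − AUC)), with weight 1/LnSE². These are pooled and exponentiated as in 5.3.2. The last column below covers trials with a significant Van Elteren test on percent change and a defined CI.

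| Input to the ROC step | Assumed log-SD | WMWodds | 95% CI includes 1 |
|---|---|---|---|
| Percent change | any | about 5.0 | about 27-32% |
| Week 8 CK | 0.3 | 4.9 | 31% |
| Week 8 CK | 0.5 | 4.4 | 40% |
| Week 8 CK | 0.8 | 3.5 | 57% |
| Week 8 CK | 1.0 | 3.0 | 64% |
| Week 8 CK | 1.3 | 2.6 | 73% |

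Strata of 4+8 per arm give much the same for Week 8 CK: 37%, 57%, 64% and 74% at log-SD 0.5, 0.8, 1.0 and 1.3. Moving the median between 3000 and 8000 U/L changes the WMWodds little: 4.4-4.5 at log-SD 0.5, 2.9-3.3 at 1.0 and 2.5-2.8 at 1.3.

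**5. Single trials.** The level-based AUC exceeded the percent-change AUC in 35% of simulated trials at log-SD 0.5 and in 12% at 1.3. The dilution is an average effect.

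**The case against.** A reader might infer that the SAP has decided to report the WMWodds on raw Week 8 CK. The documents do not support that. SAP 5.3.2 opens by pointing to Section 2.1, where the WMWodds is defined under a null on percent change. The SAP also uses CK levels as a loose name for the parameter: 5.1.1.8.1 describes the trimmed-means analysis by reference to CK levels, and 5.3.3 defines that same analysis on percent change. 5.3.2 names no variable for the Van Elteren test or the Hodges–Lehmann estimate either, and nobody doubts that those use percent change. Without a visit, the literal instruction cannot even be run as it stands. The table specifications are in a separate document that may settle the matter.

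All of this stands as evidence of intent, but it does not make the step safe. Where the endpoint sections mean change they say so, and in 5.3.4 (E) CK levels within the normal range means the raw value.

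A reader might also infer that the literal reading creates the disagreement between p-value and CI, or that correcting it would remove the disagreement. Neither follows. Even on percent change, the SAP's interval includes 1 in about 27-32% of trials with a significant test, because it is wide in such small strata. It is also undefined when a stratum separates completely, since LnSE then divides by zero. On percent change that happens in at least one stratum in about 17% of trials at 6+6 per arm. That is a separate matter from the variable named.

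**Conclusion.** The conflict is real and should be reconciled: the calculation step names a variable, and leaves out a visit, in a way that does not match the hypothesis, endpoint, estimand or protocol. It is a wording conflict with a probable intended meaning. The documents do not establish a switch of variable.

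The consequence of a literal implementation depends on baseline CK spread, which the documents do not give. It is negligible at a log-SD of 0.3 (4.9 against 5.0), and at 1.3 the average WMWodds is roughly halved (2.6). The extra share of significant trials whose CI includes 1 runs from almost none to about 40 percentage points or more (73% against 27-32%). These figures rest on the planning model, the log-normal baseline and the assumed strata. One trial could move either way.

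The primary p-value, the roughly 95% power and the testing hierarchy do not depend on this sentence, and it does not govern the Hodges–Lehmann estimate. What is at stake is the correctness of one of the two reported magnitudes for the primary endpoint, and of the supplementary analyses that reuse it.

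**What to change.** In SAP 5.3.2, replace the step with: *For each stratum the WMWodds will be calculated via ROC analysis of the percentage change from baseline in CK at Week 8 (%CHG, Section 5.3.1).* State the direction of the AUC, for example as the probability that a zilucoplan patient has the lower (more negative) change, so that a value above 1 favors zilucoplan. Use the same wording for the unweighted WMWodds and, with Week 4 in place of Week 8, for 5.3.4 (A). Check that the table specifications and the program use the same input.

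The cost is a few words and the input variable of one procedure call. No new data, assessment or sample-size change is needed.

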5.3.3 Sensitivity analyses

Analysis based on Van Elteren test and on trimmed means methodology (Permutt 2017) in ITT if at Week 8 at least 15% of participants do not have evaluable CK results. All missing data will be

imputed at an extreme unfavorable value. A permutation-based test will be carried out, with the trimming fraction applied adaptively at 1000 treatment permutations. The fraction trimmed will be chosen adaptively as that greatest of the proportion of missings in the group.

First, data should be ordered and trimmed by equal fractions, always trimming all drop outs. Then, the summary measure will be computed based on the trimmed data. Previous steps to be repeated on permuted data to construct a reference distribution for testing and interval estimation.

Estimand:

- Treatment: Zilucoplan administered by daily subcutaneous (SC) injection (0.3 mg/kg) vs matching placebo
- Target Population: is defined through the inclusion/exclusion criteria at Sections 8.1 and 8.2 of the study protocol reflecting the targeted IMNM population
- Endpoint: percentage change from baseline to Week 8 in CK levels
- Intercurrent event: regardless of any treatment discontinuation for any reason; censoring after prohibited medication
- Population level summary: difference in ranks of the percentage change from baseline between treatments followed by trimmed means

5.3.4 Supplementary analyses

- Analysis methodology mentioned in Section 5.3.2 will be repeated in ITT using the LOCF approach; that is any Week 8 missing data for any reason will be imputed by the closest non-missing value of the parameter.
- Analysis methodology mentioned in Section 5.3.2 will be repeated in PPS.
- Analysis methodology mentioned in Section 5.3.2 will be repeated in ITT_{NOCOVID-19}.

Further analysis within the ITT population, based on the percentage change of CK levels from baseline to Week 4 and Week 8 will be considered as indicated below:

Definition of Estimand(s):

- Treatment: Zilucoplan administered by daily subcutaneous (SC) injection (0.3 mg/kg) vs matching placebo
- Target Population: is defined through the inclusion/exclusion criteria at Sections 8.1 and 8.2 of the study protocol reflecting the targeted IMNM population
- Endpoints:
 - (A): percentage change from baseline to Week 4 in CK levels
 - (B): change from baseline to Week 4 and to Week 8 in Log_{10}CK levels
 - (C): Week 4 and Week 8 response defined as at least 80% reduction in CK levels

- (D): Week 4 and Week 8 response defined as at least 50% reduction in CK levels
- (E) Week 4 and Week 8 CK levels within normal range
- Intercurrent events: regardless of treatment discontinuation due to lack of efficacy, or any AE, death; censoring after prohibited medication
- Population level summary:
 - (A): difference in ranks of the percentage change from baseline between treatment conditions followed by the Wilcoxon-Mann-Whitney odds (WMWodds) and Hodges– Lehmann estimator;
 - (B): difference in mean change from baseline to Week 4 and Week 8 of Log10CK between treatment conditions;
 - (C), (D), (E): OR of response proportion categories between treatment conditions;

For the population level summary (A): analysis will be performed as described in Section 5.3.2.

For the population level summary (B): analysis will be based on linear mixed effects model. As response variable will be the change from baseline to Week 4 and to Week 8 respectively. Treatment and strata will be fitted as fixed factors whereas baseline levels of the parameter as covariate; participants will be fitted at random. The Kenward-Roger approximation will be used to estimate the denominator's degrees of freedom. The antilogs of the least squares means (LSMs) of each IMP and the least squares mean differences (LSMDs) between the Zilucoplan and placebo will be reported for the Week 8 and Week 4 change from baseline, along with the corresponding 2-sided 95% CIs and p-values.

For the population level summary (C, D, E): Analysis will be performed via logistic regression model with treatment and stratification factors included for each response parameter; the OR of Zilucoplan over placebo will be given followed by the 95% CI.

Corresponding summary statistics will be presented in each IMP.

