		Data description and precision rules	Update to meet UCB Standards / Template
		Text is added to describe analyses for all efficacy endpoints and list the estimand attributes	To align with the protocol amendment 2, dated 16 February 2021
		Abbreviation List is updated	Ensure abbreviations are used in the appropriate way
		Addition of populations: ITT No COVID-19 Safety Set No Covid-19 Additional summaries based on COVID-19 subgroups, pre or during the COVID-19 pandemic	Update analysis to include COVID-19 strategy
		The following populations are defined: Enrolled Set Intention to Treat Extension Pharmacodynamic Per-Protocol Set Pharmacokinetic Per-Protocol Set	To capture all the analysis populations
		RA101495 Safety Population is deleted	Information is redundant
		Disposition on all participants enrolled and screen failures is defined	To display the disposition of screen failures as per UCB guidance
		Definition of treatment exposure is added	Information was missing
		Categories of prior and concomitant medications are defined	Further clarification
		Age and BMI cutoffs are introduced in the summary statistics	To describe the parameters summarized in more details

SAP Version	Approval Date	Change	Rationale
		Demographics and baseline characteristics will not be compared between IMPs	To map the UCB policy
		Summaries on Related of IMNM and non-IMNM related medications are added	To describe the parameters summarized in more details
		Analysis based the Van Elteren test is upgrade to primary analysis	To align with protocol amendment 2, dated 16 February 2021
		Wilcoxon Mann Whitney Odds estimation Hodges–Lehmann estimator are added.	To align with the protocol amendment 2, dated 16 February 2021
		Main analysis of the primary and secondary efficacy endpoints is changed from the Last Observation Carried Forward approach (LOCF) to observed case analysis. LOCF was downgraded to supplementary analysis.	To follow the treatment policy of the study estimands based on the protocol amendment 2, dated 16 February 2021
		Separate Wilcoxon signed rank tests for each IPM will not be implemented	Information is not relevant
		The following text has been deleted: “No control for multiplicity will be applied for the secondary endpoint analyses in this Phase 2 study”	Team’s decision
		Secondary endpoints are re-ordered to define the hierarchy and setting the multiplicity controls	To control multiplicity

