^q The pharmacogenomic sample may be collected at any study visit.

^r Dosing on study visit days should be held until clinical assessment and blood collection has been completed.

Table 1-3: Schedule of Assessments During the Extension Portion of the Study

	Month 2			Month 3	Month 4	Month 5	Month 6	Visits after Day E117			
Study Procedure	Day E1 ^a (Day 57)	Day E8 (±2 days)	Day E15 (±2 days)	Day E29 (±2 days)	Day E57 (±2 days)	Day E87 (±7 days)	Day E117 (±7 days)	Each Month (±7 days)	Every 3 Months (±7 days)	Final Extension Visit ^b	Safety Follow-up Visit (last dose + 40d)
Informed consent	X										
Review eligibility and randomization	X										
Weight	X			X	X		X		X	X	
Prior and concomitant medications	X	X	X	X	X	†	X	X	X	X	X
Safety											
Physical examination	X	X	X	X	†		X		X	X	X
Vital signs ^c	X	X	X	X	X		X		X	X	X
12-lead ECG	X				X				X		
Neisseria meningitidis vaccination ^d	X	Standard of Care	Standard of Care	Standard of Care	Standard of Care	Standard of Care	Standard of Care	Standard of Care			
Hematology / Chemistry / CK ^e	X	X	X	X	X		X		X	X	
Coagulation ^{e,f}	X	X	X	X	X		X		X	X	
Urinalysis ^e	X	X	X	X	X		X		X	X	
Pregnancy test ^g	X	X	X	X	X	X	X	X	X	X	X
Adverse Events ^h	X	X	X	X	X	X	X	X	X	X	X ^h
Anti-Drug Antibody ^e	X	X		X	X		X		X	X	
Efficacy											

Table 1-3: Schedule of Assessments During the Extension Portion of the Study

	Month 2			Month 3	Month 4	Month 5	Month 6	Visits after Day E117			
Study Procedure	Day E1 ^a (Day 57)	Day E8 (±2 days)	Day E15 (±2 days)	Day E29 (±2 days)	Day E57 (±2 days)	Day E87 (±7 days)	Day E117 (±7 days)	Each Month (±7 days)	Every 3 Months (±7 days)	Final Extension Visit ^b	Safety Follow-up Visit (last dose + 40d)
3TUG ^{i,j}	X			X	X		X		X	X	
Proximal MMT ⁱ	X			X	X		X		X	X	
Physician Global Activity VAS ⁱ	X			X	X		X		X	X	
Patient Global Activity VAS ⁱ	X			X	X		X		X	X	
HAQ ⁱ	X			X	X		X		X	X	
MDAAT ⁱ	X			X	X		X		X	X	
FACIT-Fatigue ⁱ	X			X	X		X		X	X	
Pharmacokinetic / Pharmacodynamic											
Zilucoplan plasma PK ^k	X	X	X	X	X		X		X	X	
Pharmacodynamic analysis ^k	X	X	X	X	X		X		X	X	
Exploratory											
Autoantibodies testing	X			X	X		X		X	X	
Biomarker testing ^l	X	X	X	X	X		X		X	X	
Study Drug											
Zilucoplan or placebo administration ^m	X	X	X	X	X	X	X	X	X	X	

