- Minimum and maximum will have the same number of decimal places as the original value reported.

Derived variables in general will be displayed to 1 more decimal place than the variables used in the derivation. If the number of decimal places reported in the raw data is varied, then either the maximum raw number of reported decimal places or 3 will be used, whichever is the lowest.

If no participants have data at a given time point, for example, then only n=0 will be presented. However, if n<3, present the n, minimum and maximum only. If n=3, n, mean, median, minimum and maximum will be presented only. The other descriptive statistics will be left blank.

If for a particular output there are no valid cases to summarize for any variable, then report “No data observed”.

Demographics and baseline characteristics will be analyzed in ITT. Separate tables based on the enrollment date relative to 11 Mar 2020 will be created.

Efficacy analyses will be performed primarily in the ITT population. Prior and Concomitant medications summaries will be performed in the SS. Medical History will be analyzed in the ITT. Safety, PK and PD analyses will be performed primarily in the SS, PK-PPS and PD-PPS.

Comparative efficacy analysis (inferential statistics) will focus on the Main Portion of the study only where both active and placebo treatments are given in blinded manner.

Baseline is defined in Section [5.1.1.2.4](#).

Change from Baseline is defined as: post baseline value - baseline value.

Percentage Change from Baseline is defined as: $100 \times (\text{Change from Baseline}/\text{Baseline})$, if baseline is greater than zero.

IEs are defined as these events that may preclude an observation from the study or affect the interpretation of the results; in the current setting the following is considered as IE:

- Intake of medication which is prohibited by the protocol (complement inhibitor, rituximab, statins, or any investigational medicinal product while on study)

Since the primary analysis of the primary and secondary endpoints will be based on treatment policy estimand (that is, observed case analysis) the only data manipulation to be considered is the censoring of efficacy values following to the administration of any prohibited medication.

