5.1.1.2.4 Definition of Baseline values

Unless otherwise specified, the Baseline value for the Treatment Period is defined as the most recent (date/time considered) non-missing value obtained prior to the administration of the first study dose. If there are multiple assessments on that day then the time will be considered for the selection of the appropriate measurement. For parameters with no Baseline value as per schedule of assessments the screening value will be set as Baseline value. If a Baseline measurement is not available but an unscheduled measurement occurs after the planned Baseline measurement time point but before dosing, then the unscheduled measurement will be used.

For participants who received placebo in the Treatment Period, the value obtained prior to the first administration of Zilucoplan will occur on the Day E1 (Day 57) visit during the Extension Portion of the study and this will be the Baseline value for them for any summary tables during the Extension Portion of the study. If Day 57 dose is missing the last non-missing dose on placebo during the Main Portion will define the baseline date for the placebo patients who change to active in Extension Portion.

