5.4.5 Supplementary analyses

Analysis mentioned at Section 5.4.3 will be repeated in ITT with missing values imputed based on the LOCF approach from the previous non missing visit of Week 8. Based on this approach, the elements of ACR/EULAR will also be imputed with the last non missing parameter in order the score to be calculated at Week 8.

Analysis mentioned at Section 5.4.3 will be repeated in the ITT_{NOCOVID-19}. In case of non-convergence, only the summary statistics will be reported.

Analysis mentioned at Section 5.4.3 will be repeated in the PPS.

Estimand:

- Treatment: Zilucoplan administered by daily subcutaneous (SC) injection (0.3 mg/kg) vs matching placebo
- Target Population: is defined through the inclusion/exclusion criteria at Sections 8.1 and 8.2 of the study protocol reflecting the targeted IMNM population
- Endpoints:
 - ACR/EULAR of at least minimal response at Week 4;
 - ACR/EULAR ordinal treatment response at Week 4 and Week 8;
 - ACR/EULAR Total Improvement Score at Week 4 and Week 8;
 - Change from Baseline to Week 4 in Triple Timed Up and Go (3TUG) Test (in ambulatory patients only);
 - Change from Baseline to Week 4 in Proximal Manual Muscle Testing (MMT);
 - Change from Baseline to Week 4 in Physician Global Activity Visual Analogue Scale (VAS);

- Change from Baseline to Week 4 in Patient Global Activity Visual Analogue Scale (VAS);
- Change from Baseline to Week 4 in Health Assessment Questionnaire (HAQ);
- Change from Baseline to Week 4 in MDAAT Extra muscular Disease Activity VAS Score;
- Change from Baseline to Week 8 in FACIT-Fatigue Scale;
- Intercurrent event: regardless of treatment discontinuation for any reason; censoring after administration of prohibited medication;
 - Population level summary: Odds Ratio (OR) of ACR/EULAR ≥ 20 response proportion between treatment conditions (analysis will be performed as mention Section 5.4.3).
 - Population level summary: ACR/EULAR ordinal treatment response proportion in treatment conditions;
 - Difference in continuous endpoint means between treatment conditions (analysis will be performed as mention Section 5.4.3).

For the determination of ACR/EULAR response categories, see Section 6.1.5.7. Ordinal ACR/EULAR treatment response (no improvement, minimal improvement, moderate improvement, major improvement) at Week4 and Week 8 will be only be summarized by IMP.

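### The supplementary LOCF analysis of CK fills a missing Week 8 value with the closest one, which read literally can be an on-zilucoplan Extension value in the placebo arm

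*SAP*

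**What the plan says.** SAP 5.3.4 (Supplementary analyses) repeats the Van Elteren, WMWodds and Hodges-Lehmann analysis of Section 5.3.2 in the ITT population under an LOCF label. It explains the label in these words: "any Week 8 missing data for any reason will be imputed by the closest non-missing value of the parameter". It states no direction in time, no restriction to the Main Portion and no rule for ties.

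SAP 5.4.5 describes the matching analysis of the secondary endpoints differently. There, missing values are "imputed based on the LOCF approach from the previous non missing visit of Week 8".

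The status of the analysis is clear. The SAP version history records that "LOCF was downgraded to supplementary analysis", and SAP 5.1 bases the main analysis on the data as collected ("that is, observed case analysis"), apart from censoring after prohibited medication. SAP 5.1 also says: "Comparative efficacy analysis (inferential statistics) will focus on the Main Portion of the study only".

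In SAP Tables 1-2 and 1-3, the row "Hematology / Chemistry / CK" is marked at Week 4 (Day 29), at Week 8 (Day 57, which is also Day E1) and at Day E8. For participants on placebo in the Main Portion, SAP 5.1.1.2.4 says that "the value obtained prior to the first administration of Zilucoplan will occur on the Day E1 (Day 57) visit".

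**The concern.** Carrying an observation forward means using an earlier value. A closest-value rule can look ahead, and on this schedule the nearest scheduled CK to a missing Day 57 sample lies ahead, in the Extension. For a participant randomised to placebo, that value follows the switch to zilucoplan. For a participant randomised to zilucoplan, it is simply another on-zilucoplan value. Any early drug effect on CK therefore enters the placebo arm only and narrows the difference.

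The analysis is supplementary, but it has a job. The trimmed-means sensitivity analysis in SAP 5.3.3 runs only if at least 15% of participants lack an evaluable Week 8 CK. Since 0.15 × 24 = 3.6, that means at least 4 of 24. With 1 to 3 missing, LOCF is the only prespecified analysis of the primary endpoint that fills in missing values; the per-protocol and no-COVID-19 repeats only change the population. A diluted LOCF result could make a sound main result look fragile.

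The pattern is possible. SAP 5.1.1.8.2 expects missing data because of COVID-19. Protocol 7.4 allows remote follow-up with couriered drug and assessments recorded as not done.

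**Working it through.** **Which value is closest**

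- Week 4 is Day 29 ± 2, Week 8 is Day 57 ± 7, and Day E8 is ± 2 days (SAP Tables 1-2 and 1-3). Day E1 is Day 57, so Day E8 is nominally Day 64.
- Week 4 to Week 8: 57 − 29 = 28 days. Across the windows this is 50 − 31 = 19 to 64 − 27 = 37 days.
- Day E1 to Day E8: 64 − 57 = 7 days, or 5 to 9 with the window.
- Day E8 is nearer than Week 4 for every combination of scheduled visits.
- Daily dosing from Day E1 and a pre-dose sample on Day E8 give about 7 zilucoplan doses before that sample.

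**Reproducing the stated power**

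Inputs from SAP Section 3: 12 per arm; Wilcoxon rank sum test at two-sided 0.05; active reduction with mean 80%, SD 8%; 4 placebo participants like active; 8 with mean 10%, SD 8%.

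- The exact null distribution for 12 versus 12 rejects at U ≤ 37 or U ≥ 107 (actual two-sided level 0.0449).
- The 8 low placebo values fall below essentially all active values: 8 × 12 = 96 pairs.
- The other 4 are exchangeable with the 12 active values and contribute U′, which follows the 4-versus-12 null distribution.
- Power = P(96 + U′ ≥ 107) = 94.8%, which agrees with the stated 95%.
- π = (96 + 4 × 12 × 0.5)/144 = 120/144, so WMWodds = 120/24 = 5.0.

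**Upper bound: Day E8 CK fully active-like (assumption: mean 80%, SD 8%)**

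Each affected non-responder moves from the low group to the active-like group.

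| Affected non-responders | Rejection needs | Exact power | WMWodds | Mean Hodges-Lehmann shift (points) |
|---|---|---|---|---|
| 0 | 96 + U′ ≥ 107 | 94.8% | 120/24 = 5.0 | about 63 |
| 1 | 84 + U′ ≥ 107 | 77.9% | 114/30 = 3.8 | about 58 |
| 2 | 72 + U′ ≥ 107 | 55.4% | 108/36 = 3.0 | about 35 |
| 3 | 60 + U′ ≥ 107 | 35.5% | 102/42 = 2.4 | about 12 |

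The Hodges-Lehmann figures are simulation averages; power and WMWodds are exact under the model.

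**Partial response by Day E8 (assumption: mean fall 30% or 45%, SD 8%)**

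A value with mean 45% still sits below almost every active value: (80 − 45)/√(8² + 8²) = 35/11.3 = 3.1 standard deviations. A rank measure therefore hardly moves. In 20,000 simulated trials with 1 to 3 affected, power stayed at about 95% and WMWodds at about 5.0. The Hodges-Lehmann shift fell from about 63 to about 59 points (one affected), 49 to 56 (two) or 39 to 52 (three).

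**No response by Day E8, or Week 4 used instead**

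With a mean fall of 10% at Day E8, nothing changes. If Week 4 is carried forward and is assumed to behave like Week 8, power stays at 94.8% and WMWodds at 5.0.

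**The case against.** The best defence is that LOCF has a settled meaning and the SAP spells out the abbreviation, so a Day E8 value cannot be carried forward to Day 57. The rest of the SAP points the same way: comparative analysis centres on the Main Portion, the Treatment Period ends at the Week 8 visit (5.1.1.2.2), and Extension efficacy is shown under separate switch groups (5.1.1.4). A careful programmer might use Week 4 without asking. This stands in part. It makes a backward reading reasonable, so a reader who infers that the SAP certainly puts on-drug values into the placebo arm goes too far. It does not remove the problem. The operative wording after the label says something else, Section 5.4.5 shows that the authors could write the backward rule, and no section bars Extension values from filling a Week 8 gap.

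The second defence is that the pattern is rare. This also stands. It needs a placebo participant who enters the Extension without a Day 57 CK and has a Day E8 CK. Anyone who stops drug before Week 8 cannot enter, entry requires completing the Main Portion, and Day 57 and Day E1 are one visit at which CK is scheduled. An unscheduled CK nearer to Day 57 would displace either value.

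Third, the power losses are a bound. They need a full 80% fall within a week, for which the documents give no figure, and they need the affected person to be one of the 8 non-responders. They also use an unstratified test, whereas Section 5.3.2 specifies Van Elteren.

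**Conclusion.** The rule in SAP 5.3.4 is wrong as worded for an LOCF analysis and inconsistent with 5.4.5. Read literally, it selects Day E8 over Week 4 for a placebo participant in the Extension with no Day 57 CK, and any bias is toward no difference.

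The size ranges from nil to material. It is nil if CK has not responded by Day E8. With a mean fall of 30% to 45% it is confined to the Hodges-Lehmann shift. At the upper bound, power is 78% or 55% and WMWodds 3.8 or 3.0 with one or two affected non-responders. How many participants would be affected cannot be estimated from the documents.

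A reader might infer that the primary result is contaminated or that the trial's power falls below 95%. Neither follows. The main analysis is observed case, no LOCF test enters the testing hierarchy of SAP Section 2, and the stated power is not a claim about this supplementary analysis.

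**What to change.** In SAP 5.3.4, replace the closest-value rule with this: a missing Week 8 CK takes the last non-missing post-baseline value obtained on or before the Week 8 (Day 57) pre-dose sample, before any Extension dose and before any prohibited medication. Word 5.4.5 the same way, so that the SAP holds one LOCF definition. The cost is one sentence. It needs no new data and no change to the main analysis, and it should be made before unblinding.
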